11.8 Appendix 8. Additional Guidance for Tumor Lysis Syndrome

11.8.1 Recommendations for Initial Management of Electrolyte Abnormalities and Prevention of Tumor Lysis Syndrome (TLS)

All subjects will receive TLS prophylaxis as described in Section 6.1.4.1. Allopurinol or equivalent should be used to reduce uric acid level. This should be initiated at least 72 hours prior to dosing. Treatment may need to be continued for up to 5 weeks.

Other agents to reduce uric acid level, such as rasburicase, may be used per investigator discretion and institutional guidelines.

Allopurinol is unapproved for TLS prophylaxis in Japan.

Within the first 24 hours after either the first dose or dose escalation, if any laboratory criteria below are met, no additional AMG 176 doses should be administered until resolution. A rapidly rising serum potassium is a medical emergency.

Nephrology (or other acute dialysis service) should be contacted/consulted (per institutional guidelines to ensure emergency dialysis is available) on admission for any subject hospitalized prophylactically or in response to laboratory changes.

Intravenous (IV) fluids (eg, D5 1/2 normal saline) should be initiated at a rate of at least 1 mL/kg/hr rounded to the nearest 10 mL (target 150 to 200 mL/hr; not < 50 mL/hr). Modification of fluid rate should also be considered for individuals with specific medical needs.

Monitor for symptoms or signs of TLS (eg, fever, chills, tachycardia, nausea, vomiting, diarrhea, diaphoresis, hypotension, muscle aches, weakness, paresthesias, mental status changes, confusion and seizures). If any clinical features are observed, recheck potassium, phosphorus, uric acid, calcium, and creatinine within 1 hour and perform electrocardiogram (ECG).

Vital signs should be taken at time of all blood draws or any intervention.

The management recommendations below focus on the minimum initial responses required (Roberts et al, 2016). If a diagnosis of TLS is established, ongoing intensive monitoring and multi-disciplinary management will be per institutional protocols.

Abnormality	Management Recommendations
Hyperkalemia (including rapidly rising potassium)	
• Potassium \geq 0.5 mmol/L increase from prior value (even if potassium within normal limits)	
• Recheck potassium, phosphorus, uric acid, calcium and creatinine in 1-hour STAT. If further \geq 0.2 mmol/L increase in potassium, but still $<$ upper limit of normal (ULN), manage as per potassium \geq ULN. Otherwise recheck in 1 hour.• Resume per protocol testing if change in potassium is $<$ 0.2 mmol/L, and potassium $<$ ULN, and no other evidence of tumor lysis.• At discretion of investigator, may recheck prior to hospitalization. If stable or decreased, and still within normal limits, hospitalization is at discretion of the investigator. Potassium phosphorus, uric acid, calcium and creatinine must be rechecked within 24 hours.
• Potassium $>$ upper limit of normal	
• Perform STAT ECG and commence telemetry.• Nephrology notification with consideration of initiating dialysis.• Administer Kayexalate 60 g (or Resonium A 60 g).• Administer furosemide 20 mg IV \times 1• Administer calcium gluconate 100-200 mg/kg IV slowly if there is ECG/telemetry evidence of life-threatening arrhythmias.• Recheck potassium, phosphorus, uric acid, calcium and creatinine in 1 hour STAT.
– If potassium $<$ ULN 1 hour later, repeat potassium phosphorus, uric acid, calcium and creatinine 1, 2, and 4 hours, if no other evidence of tumor lysis.
• Potassium \geq 6.0 mmol/L (6.0 mEq/L) and/or symptomatic (eg, muscle cramps, weakness, paresthesias, nausea, vomiting, diarrhea)	
• Perform STAT ECG and commence telemetry.• Nephrology (or other acute dialysis service) assessment with consideration of initiating dialysis.• Administer Kayexalate 60 g (or Resonium A 60 g).• Administer furosemide 20 mg IV \times 1.• Administer insulin 0.1 U/kg IV + D25 2 mL/kg IV.• Administer sodium bicarbonate 1 to 2 mEq/kg IV push.
– If sodium bicarbonate is used, rasburicase should not be used as this may exacerbate calcium phosphate precipitation.• Administer calcium gluconate 100 to 200 mg/kg IV slowly if there is ECG/telemetry evidence of life-threatening arrhythmias. Do not administer in same IV line as sodium bicarbonate.• Recheck potassium, phosphorus, uric acid, calcium and creatinine every hour STAT.

Hyperuricemia	
• Uric acid \geq 8.0 mg/dL (476 μ mol/L)	
 Consider rasburicase (0.2 mg/kg as an intravenous infusion over 30 minutes). 
 If rasburicase is used, sodium bicarbonate should not be used as this may exacerbate calcium phosphate precipitation. Recheck potassium, phosphorus, uric acid, calcium and creatinine in 1-hour STAT.
• Uric acid \geq 10 mg/dL (595 μ mol/L) OR • Uric acid \geq 8.0 mg/dL (476 μ mol/L) with 25% increase and creatinine increase \geq 0.3 mg/dL (\geq 0.027 mmol/L) from pre-dose level	
 Administer rasburicase (0.2 mg/kg as an intravenous infusion over 30 minutes). 
 When rasburicase is used, sodium bicarbonate should not be used as this may exacerbate calcium phosphate precipitation. Consult nephrology (or other acute dialysis service). Recheck potassium, phosphorus, uric acid, calcium and creatinine in 1-hour STAT. If uric acid $<$ 8.0 mg/dL 1 hour later, repeat potassium, phosphorus, uric acid, calcium and creatinine 2 and 4 hours later, if no other evidence of tumor lysis
Hypocalcemia	
• Calcium \leq 7.0 mg/dL (1.75 mmol/L) 
 AND • Patient symptomatic (eg, muscle cramps, hypotension, tetany, cardiac arrhythmias)	
 Administer calcium gluconate 50 to 100 mg/kg IV slowly with ECG monitoring. Telemetry. Recheck potassium, phosphorus, uric acid, calcium and creatinine in 1-hour STAT. If calcium normalized 1 hour later, repeat potassium, phosphorus, uric acid, calcium and creatinine 2 and 4 hours later, if no other evidence of tumor lysis. Calculate corrected calcium and check ionized calcium if albumin low.
Hyperphosphatemia	
• Phosphorus \geq 5.0 mg/dL (1.615 mmol/L) with \geq 0.5 mg/dL (0.16 mmol/L) increase	
 Administer a phosphate binder (eg, aluminum hydroxide, calcium carbonate, sevelamer hydroxide, or lanthanum carbonate). Nephrology (or other acute dialysis service) notification (dialysis required for phosphorus uric \geq 10 mg/dL). Recheck potassium, phosphorus, uric acid, calcium and creatinine in 1 hour STAT. If phosphorus $<$ 5.0 mg/dL 1 hour later, repeat potassium, phosphorus, uric acid, calcium and creatinine 2 and 4 hours later, if no other evidence of tumor lysis.
Creatinine	
• Increase \geq 25% from baseline	
 Start or increase rate of IV fluids. Recheck potassium, phosphorus, uric acid, calcium and creatinine in 1 to 2 hours STAT.

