- Monitoring of electrolyte values is required prior to dosing anytime a dose is higher than one previously given to the subject. This will include at the following times:
 - Prior to the week 1, day 1 dose
 - Prior to each dose during the ramp-up period
 - Prior to the initial dosing at the target dose level
- Prior to administering these doses, all electrolyte values (including LDH, potassium, uric acid, phosphorus, calcium and creatinine) must be reviewed and within normal range (samples must be drawn within 24 hours prior to dosing of AMG 176). The investigator's decision to proceed with AMG 176 treatment initiation will be based on these laboratory values.

Within the first 24 hours after either the first dose or dose escalation, if any laboratory criteria for TLS are met, no additional AMG 176 doses should be administered until resolution. A rapidly rising serum potassium is a medical emergency.

Prophylactic dose reductions for potassium, phosphorus and/or uric acid values at the high end of normal range should be considered.

If the potassium, uric acid, inorganic phosphate and/or creatinine values are higher than the normal range or the calcium is lower or higher than the normal range, this (these) value(s) can be approved following a discussion between the Amgen medical monitor and investigator.

On the AMG 176 dosing days chemistry labs must be performed pre-dose (within 4 hours before AMG 176 administration), 2, 4, 8, 12 and 24 hours after the start of AMG 176 infusion. Pre-dose labs will be used as baseline to assess potential

electrolytes abnormalities occurring post AMG 176 administration. These labs must be reviewed in real time by the investigator.

Day 2 dosing of AMG 176 (BIW schedule) should not be administered until the 24 hours post dose laboratory values are reviewed by the investigator.

All 24-hour laboratory assessments may be taken \pm 2 hours, if necessary.

Monitor for signs and symptoms of TLS (eg, fever, chills, tachycardia, nausea, vomiting, diarrhea, diaphoresis, hypotension, muscle aches, weakness, paresthesias, mental status changes, confusion, and seizures). If any clinical features are observed, recheck potassium, phosphorus, uric acid, calcium and creatinine within 1 hour.

Additional information on the management recommendations of laboratory abnormalities can be found in Section [11.2](#).

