- Nephrology (or acute dialysis service) consultation should be considered on admission (based on investigator discretion) for hospitalized subjects per institutional guidelines to ensure emergency dialysis is available and the appropriate staff is aware and prepared.

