11.8.2 Cairo-Bishop Definition of Laboratory Tumor Lysis Syndrome

Two or more of the following criteria occurring within 3 days before or 7 days after therapy:

Element	Value	Change from Baseline	
Uric Acid	$\geq 476 \mu\text{mol/L}$ (8 mg/dL)	OR	25% increase from baseline
Potassium	$\geq 6.0 \text{ mmol/L}$ (6 mg/dL)	OR	25% increase from baseline
Inorganic phosphorus	$\geq 1.45 \text{ mmol/L}$ (4.5 mg/dL)	OR	25% increase from baseline
Calcium	$\leq 1.75 \text{ mmol/L}$ (7.0 mg/dL)	OR	25% decrease from baseline

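### The TLS guidance words its dose-hold trigger in two ways, gives mutually exclusive drug instructions in one overlap, and states two nephrology rules

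*Protocol*

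**What the plan says.** **Dose hold.** Two Protocol sections carry nearly the same sentence, both for the 24 hours following a first or an escalated dose. Section 6.1.4.1 says "if any laboratory criteria for TLS are met, no additional AMG 176 doses should be administered until resolution". Section 11.8.1 says "if any laboratory criteria below are met, no additional AMG 176 doses should be administered until resolution".

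**The two candidate lists.** Section 11.8.1 is followed by a table of single-analyte abnormalities; the first potassium row reads, from its threshold on, "0.5 mmol/L increase from prior value (even if potassium within normal limits". Section 11.8.2 is the only definition of laboratory TLS in the protocol: "Two or more of the following criteria occurring within 3 days before or 7 days after therapy", covering uric acid, potassium, phosphorus and calcium.

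**Drug instructions in the Section 11.8.1 table.** For potassium of at least 6.0 mmol/L and/or symptoms: "Administer sodium bicarbonate 1 to 2 mEq/kg IV push", with a note that rasburicase should then not be used. The upper uric acid row (at least 10 mg/dL, or at least 8.0 mg/dL with a 25% rise and a creatinine rise of at least 0.3 mg/dL) orders rasburicase and adds: "When rasburicase is used, sodium bicarbonate should not be used as this may exacerbate calcium phosphate precipitation".

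**Nephrology.** Section 11.8.1 says nephrology or another dialysis service should be contacted on admission for any subject hospitalized prophylactically. Section 6.1.4.1 says "consultation should be considered on admission (based on investigator discretion". All subjects are hospitalized for TLS monitoring (Section 6.1.4.1 and Table 1-9).

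**The concern.** TLS is one of two identified risks (Section 2.3.2), with one fatal outcome among 109 safety-evaluable subjects (Section 2.3.2.1). A site that reads only the treatment section and a site that works from the appendix may apply different hold rules to the same laboratory values.

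The hold matters most where the next dose falls at the end of the 24-hour window: day 2 of the BIW schedule, which Section 6.1.4.1 makes conditional on review of the 24-hour values, and the consecutive-day dosing of Part 5B. On the QW schedule the next dose is a week away. Held doses also count against the requirement of 75% of planned AMG 176 doses for DLT evaluability (Section 6.2.1.1).

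The drug conflict concerns an emergency instruction, where staff have little time to work out which of two rows prevails.

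**Working it through.** The plan states no figure to reproduce. The check compares the lists and runs example laboratory values through them.

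**1. The lists side by side**

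| Analyte | Section 11.8.1 table (one row is enough if *below* means this table) | Section 11.8.2 element (two or more make laboratory TLS) |
|---|---|---|
| Potassium | rise ≥ 0.5 mmol/L from prior value, even if normal; above ULN; ≥ 6.0 mmol/L and/or symptoms | ≥ 6.0 mmol/L or 25% rise |
| Uric acid | ≥ 8.0 mg/dL; upper row as given above | ≥ 8 mg/dL or 25% rise |
| Phosphorus | ≥ 5.0 mg/dL with a rise ≥ 0.5 mg/dL | ≥ 4.5 mg/dL or 25% rise |
| Calcium | ≤ 7.0 mg/dL and symptomatic | ≤ 7.0 mg/dL or 25% fall |
| Creatinine | rise ≥ 25% | not an element |

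**2. Examples for the hold** (chosen for illustration; other analytes unchanged)

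- Potassium 3.8 to 4.4 mmol/L. Rise 4.4 − 3.8 = 0.6, which is ≥ 0.5, so a table row is met. Relative rise 0.6/3.8 = 15.8%, below 25%, and 4.4 is below 6.0, so no Section 11.8.2 element is met.
- Uric acid and phosphorus each 3.0 to 3.9 mg/dL. Relative rise 0.9/3.0 = 30% for each, so two elements are met and this is laboratory TLS. Uric acid is below 8.0 and phosphorus below 5.0, so no table row is met.
- Calcium 7.0 mg/dL without symptoms, from an assumed baseline of 9.0. No table row is met; one element is met. A hold under Section 6.1.4.1 then depends on whether one element suffices.

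The first two examples give zero and two elements, so the table and the definition disagree in both directions whether the definition is applied as one element or as two.

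**3. Examples for the drug conflict** (assumed baseline uric acid 5.0 mg/dL)

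- Potassium 6.1, uric acid 10.2: both drugs are ordered and each is barred with the other.
- Potassium 6.1, uric acid 8.5 (3.5/5.0 = 70% rise), creatinine up 0.4 mg/dL: same result.
- Potassium 6.1, uric acid 8.5, no creatinine rise: rasburicase is only to be considered, so there is no forced conflict.

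**4. Reach into the DLT-evaluable set**

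A BIW cycle has six AMG 176 doses. One lost dose leaves 5/6 = 83%, still evaluable; two lost doses leave 4/6 = 67%, below 75%. The hold window opens after the first dose and after an escalation. Escalation within cycle 1 requires ramp-up, used only for targets of 180 mg/m² or more.

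- Parts 1a and 3a (BIW) are closed.
- Part 4 Cohort 5a targets 120 mg/m², so it has one window.
- Part 5 has no DLT-incidence endpoint (Section 3).

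That leaves essentially Part 4 Cohort 5b (240 mg/m² BIW), and only if two doses are lost.

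**5. Cross-references**

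For management of laboratory abnormalities, Section 6.1.4.1 sends the reader to Section 11.2 (the analyte list). For TLS mitigation, Section 2.3.2.1 sends the reader to Section 11.9 (the myeloma response criteria). Neither is the TLS appendix, so these pointers do not settle which list is meant.

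**The case against.** The strongest reply is that the hold sentences name one list. The Section 11.8.1 table is introduced as management recommendations, not as criteria; within the appendix the word *criteria* otherwise belongs to the laboratory TLS definition in Sections 11.8.2 and 11.8.3; and Section 11.8.2 also lies below the sentence. The near-identical wording suggests one copied rule. The first potassium row also fits poorly as a hold trigger: it asks for a one-hour recheck and a return to scheduled testing if the further change is under 0.2 mmol/L, potassium is below ULN and nothing else points to lysis. This reading is tenable, so the hold sentences cannot be called a proven contradiction. What remains is an ambiguous reference and a missing count.

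On the drugs, Section 11.8.1 leaves ongoing care of established TLS to institutional procedures, and both rows involve nephrology or a dialysis service. But the table sets the minimum initial response, and for that no precedence is given.

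On nephrology, both passages use *should* and mention institutional guidelines. One nonetheless directs contact for every such subject, while the other asks only that it be considered.

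The hold lasts only until resolution, non-evaluable subjects are replaced, and a subject with clinical TLS meeting the DLT criteria stays evaluable. SAP Section 10 also reports early termination, which limits the practical effect of rewording.

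**Conclusion.** The TLS guidance is internally inconsistent in three places, with different strength.

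1. **Hold trigger.** It conflicts in both directions if *below* means the Section 11.8.1 table. Otherwise it is ambiguous, and neither sentence states whether one element or the two-of-four definition applies. The consequence lies in consecutive-day dosing; the effect on DLT evaluability is small.
2. **Bicarbonate and rasburicase.** This is a contradiction on any reading, but only when the row for potassium of at least 6.0 mmol/L and/or symptoms coincides with the upper uric acid row.
3. **Nephrology.** This is a contradiction on any reading, of minor weight.

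A reader might infer that every patient with TLS receives opposing drug orders. The documents do not support that: at uric acid of at least 8.0 mg/dL alone, rasburicase is discretionary. A reader might also infer that ordinary potassium fluctuation would cost many subjects a dose. The documents give no within-subject variability, a trigger may clear at the one-hour recheck, and a trigger is not a missed dose, so no rate can be stated.

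The verdict assumes that Section 11.8.2 is what Section 6.1.4.1 means by laboratory criteria for TLS. If the table was meant there, the defect is an undefined term.

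**What to change.** Reconcile Protocol Sections 6.1.4.1, 11.8.1 and 11.8.2 as follows:

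- Both hold sentences cite one list by section or table number and state whether one criterion or two trigger the hold.
- The Section 11.8.1 table states what applies when the top potassium row and the upper uric acid row are met together.
- One nephrology statement appears in both places.
- The TLS cross-references in Sections 2.3.2.1 and 6.1.4.1 point to Section 11.8.

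Which trigger, drug order and nephrology rule stand is for the clinical team. The cost is protocol wording only, with no change to sample size or analysis. As the study ended early, the clinical study report should say which hold trigger governed any held doses.

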11.8.2 Cairo-Bishop Definition of Laboratory Tumor Lysis Syndrome

Two or more of the following criteria occurring within 3 days before or 7 days after therapy:

Element	Value	Change from Baseline	
Uric Acid	$\geq 476 \mu\text{mol/L}$ (8 mg/dL)	OR	25% increase from baseline
Potassium	$\geq 6.0 \text{ mmol/L}$ (6 mg/dL)	OR	25% increase from baseline
Inorganic phosphorus	$\geq 1.45 \text{ mmol/L}$ (4.5 mg/dL)	OR	25% increase from baseline
Calcium	$\leq 1.75 \text{ mmol/L}$ (7.0 mg/dL)	OR	25% decrease from baseline

11.8.3 Cairo-Bishop Clinical Tumor Lysis Syndrome Definition and Grading

One or more of the following, in a subject meeting criteria for laboratory TLS:

Complication	Grade					
	0	1	2	3	4	5
Creatinine ^{a, b}	Normal	$\leq 1.5 \times \text{ULN}$	$> 1.5 - 3.0 \times \text{ULN}$	$> 3.0 - 6.0 \times \text{ULN}$	$> 6.0 \times \text{ULN}$	Death
Cardiac Arrhythmia ^a	None	Intervention not indicated	Nonurgent medical intervention indicated	Symptomatic and incompletely controlled medically or controlled with device (eg, defibrillator)	Life-threatening (eg, arrhythmia associated with CHF, hypotension, syncope, shock)	Death
Seizure ^a	None	N/A	One brief, generalized seizure(s) well controlled by anticonvulsants or infrequent focal motor seizures not interfering ADL	Seizure in which consciousness is altered; poorly controlled seizure disorder; with breakthrough generalized seizures despite medical intervention	Seizure of any kind which are prolonged repetitive or difficult to control (eg, status epilepticus, intractable epilepsy)	Death

ADL = activities of daily living; CHF = congestive heart failure; N/A = not applicable;

ULN = upper limit of normal

^a Not directly or probably attributable to therapeutic agent.

^b If no institutional ULN is specified, age/sex ULN creatine may be defined as follows: Cairo-Bishop Clinical Tumor Lysis Syndrome Definition and Grading.

Note: Laboratory tumor lysis syndrome and at least one clinical complication.

References:

11.9 Appendix 9. International Myeloma Working Group Uniform Response Criteria for Multiple Myeloma (IMWG-URC)

Response Subcategory ^a	Multiple Myeloma Response Criteria
sCR ^b	
• CR as defined below and• Normal SFLC ratio and• Absence of clonal cells in bone marrow^c by immunohistochemistry or immunofluorescence^c
CR ^b	
• Negative immunofixation on the serum and urine and• Disappearance of any soft tissue plasmacytomas and• < 5% plasma cells in bone marrow^c
VGPR ^b	
• Serum and urine M-protein detectable by immunofixation but not on electrophoresis or• ≥ 90% reduction in serum M-protein with urine M-protein level < 100 mg/24 hours• If the serum and urine M-protein are not measurable, a decrease of ≥ 90% in the difference between the involved and uninvolved FLC levels required in place of the M-protein criteria. However, documentation of VGPR requires collection and analysis of 24-hour urine sample for UPEP and immunofixation and confirmed to be negative.• If present at Baseline, a ≥ 50% reduction in the size of soft tissue plasmacytomas is also required.
PR ^b	
• ≥ 50% reduction of serum M-protein and reduction in 24 hour urinary M-protein by ≥ 90% or to < 200 mg/24 h• If the serum and urine M-protein are unmeasurable, a ≥ 50% decrease in the difference between involved and uninvolved FLC levels is required in place of the M-protein criteria.• If serum and urine M-protein are not measurable, and serum free light assay is also not measurable, ≥ 50% reduction in plasma cells is required in place of M-protein, provided baseline bone marrow cell percentage was ≥ 30%• If present at Baseline, a ≥ 50% reduction in the size of soft tissue plasmacytomas is also required
MR	
• 25%-49% reduction in the level of serum M-protein and a 50%-89% reduction in 24-hour urinary M-protein, which still exceeds 200 mg per 24 hours• If the serum and urine M-protein are not measurable, a decrease of 25%-49% in the difference between involved and uninvolved FLC levels is required in place of the M-protein criteria.• If present at Baseline, a 25%-49% reduction in the size of soft tissue plasmacytomas is also required
Stable disease	
• Not meeting criteria for CR, VGPR, PR, or PD

Footnotes defined on next page

Page 1 of 2

Response	Subcategory ^a Multiple Myeloma Response Criteria
PD ^b	
Any one or more of the following:
 
• Increase of $\geq 25\%$ from lowest response value in:
➢ Serum M-component and/or (the absolute increase must be ≥ 0.5 g/dL)○ Urine M-component and/or (the absolute increase must be ≥ 200 mg/24 h)○ Only in patients without measurable serum and urine M-protein levels; the difference between involved and uninvolved FLC levels. The absolute increase must be > 10 mg/dL➢ Bone marrow plasma cell percentages (absolute percentage must be $\geq 10\%$)• Definite development of new bone lesions or soft tissue plasmacytomas or definite increase in the size of existing bone lesions or soft tissue plasmacytomas^{e, f, g}• Development of hypercalcemia (corrected serum calcium > 11.5 mg/dL or 2.65 mmol/L) that can be attributed solely to the plasma cell proliferative disorder

Page 2 of 2

Source: Durie et al, 2006; Rajkumar et al, 2011 (*modified for protocol purposes*).

CR = complete response; sCR = stringent complete response; FLC = serum light chain; MR = minor response; PD = progressive disease; PR = partial response; SFLC = serum-free light chain; SPEP = serum protein electrophoresis; UPEP = urine protein electrophoresis; VGPR = very good partial response

Note: Patients with measurable disease in both serum (SPEP) and urine (UPEP) at study entry are required to meet response criteria in both UPEP and SPEP in order to qualify for a MR or better. Conversely, it should be noted criteria for PD only needs to be met, and confirmed, in 1 parameter. For patients without measurable protein on UPEP at Baseline, UPEP will need to be repeated to confirm a response.

^a Patients with measurable disease in both serum (SPEP) and urine (UPEP) at study entry are required to meet response criteria in both UPEP and SPEP in order to qualify for a MR or better. Conversely, it should be noted that criteria for PD only needs to be met, and confirmed, in one parameter.

^b All response categories (CR, sCR, VGPR, PR) require 2 consecutive assessments made at any time before the institution of any new therapy, as well as no known evidence of progressive or new bone lesions if radiographic studies were performed. Radiographic studies are not required to satisfy these response requirements. Bone marrow, plasmacytoma, and skeletal survey assessments are not required to be confirmed by repeat testing. SD requires a duration of ≥ 6 weeks.

^c Presence/absence of clonal cells is based upon the κ/λ ratio. An abnormal κ/λ ratio by immunohistochemistry and/or immunofluorescence requires a minimum of 100 plasma cells for analysis. An abnormal ratio reflecting presence of an abnormal clone is κ/λ of $> 4:1$ or $< 1:2$.

^d Determination of PD while on study requires 2 consecutive assessments made at any time before classification of PD and/or the institution of new therapy. Serum M-component increases of ≥ 1 g/dL from nadir are sufficient to define progression if nadir M-component is ≥ 5 g/dL.

^e Plasmacytomas: A definite increase in the size is defined as a $\geq 50\%$ increase as measured serially by the sum of the products of the cross-diameters of the measurable lesion. A plasmacytoma is considered measurable if the longest diameter is at least 1 cm and the product of the cross diameters is at least 1 cm². Plasmacytomas of lesser size will be considered non-measurable.

^f The requirement for bi-directional measurements applies only to plasmacytomas.

^g The plasmacytoma specifications for PD are based on interpretation of the IMWG-URC and practical considerations for study execution.

